3.2 Secondary objectives

Secondary objectives are to test the feasibility of data collection procedures (completeness and summary statistics) for the following measures:

Page 21 of 60

- Measures at baseline (demographics, smoking, alcohol, and substance abuse)
- Body weight and BMI
- Eating disorder psychopathology
- General psychopathology
- Health economic and quality of life assessment completed by both participants and their carers
- Drug adherence (to examine different methods to measure adherence (questionnaire, pill count, olanzapine plasma level)
- Drug safety (to examine the quality of reporting of adverse events)

Also to use qualitative methods to assess willingness to participate in a blinded, placebo-controlled RCT

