7.10 Withdrawal criteria

The physician responsible for a patient can withdraw a patient from a trial or a certain aspect of the trial any time for appropriate medical reasons, be they individual adverse events or new information gained about a treatment. Trial participants also have the liberty to withdraw their consent at any time and for any reason.

A patient should stop olanzapine treatment if they show:

- If they show a QTc interval >500 ms in the ECG
- If they show rises by more than 60 msec from baseline [47] in the ECG
- Severe cardiac problems
- Serious Adverse Events (SAE) An SAE will be a withdrawal criterion if it is deemed to be related to the treatment with olanzapine by the Principal Investigator
- Serious Adverse Reaction (SAR)
- Suspected Unexpected Serious Adverse Reaction (SUSAR)

However, should a patient stop olanzapine, the patient is not necessary withdrawn from the study, every effort should be made to continue to obtain follow up data as long as the participant is willing.

The whole trial will stop in case of:

- A QTc interval >500 ms in the ECG or rises by more than 60 msec from baseline or other severe cardiac side effects in more than one patient
- Serious self-harm or suicidal behaviour in more than one patient. Serious self-harm is defined as the following:
 - Recent (within the last 12 months) self-harm with suicidal intent
 - Recent self-harm with the risk to a person's own life (e.g., drug intake, deep cutting, burning, swallowing sharp items)

• Recent self-harm which could lead, or has led, to long lasting impairment of one's health and functioning

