9 PHARMACOVIGILANCE

9.1 Definitions

The Medicines for Human Use (Clinical Trials) Regulations 2004 and Amended Regulations 2006 gives the following definitions:

- Adverse Event (AE): Any untoward medical occurrence in a participant to whom a medicinal product has been administered, including occurrences which are not necessarily caused by or related to that product.
- Adverse Reaction (AR): Any untoward and unintended response in a participant to an investigational medicinal product which is related to any dose administered to that participant.
- **Unexpected Adverse Reaction (UAR)**: An adverse reaction the nature and severity of which is not consistent with the information about the medicinal product in question set out in:

The summary of product characteristics (SmPC) for that product (for products with a marketing authorisation)

- Serious adverse Event (SAE), Serious Adverse Reaction (SAR) or Suspected Unexpected Serious Adverse Reaction (SUSAR): Any adverse event, adverse reaction, or unexpected adverse reaction, respectively, that:
 - results in death;
 - is life-threatening;

- required hospitalisation or prolongation of existing hospitalisation;
- results in persistent or significant disability or incapacity;
- consists of a congenital anomaly or birth defect.
- **Important Medical Events (IME) & Pregnancy:** Events that may not be immediately lifethreatening or result in death or hospitalisation but may jeopardise the participant or may require intervention to prevent one of the other outcomes listed in the definition above should also be considered serious. Although not a serious adverse event, any unplanned pregnancy will also be reported. In case of a pregnancy, study medication will stop. The pregnant study participant will be followed up until 12 months after baseline.

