9.2 Recording and reporting of SAEs, SARs AND SUSARs

Reporting Responsibilities

All SAEs will be reported immediately to the Chief Investigator and to the Sponsor (excepting those specified in this protocol as not requiring reporting)

- All SAEs will be reported to the main REC where in the opinion of Chief Investigator (CI) the event was:
 - related that is, it resulted from administration of any of the research procedures, and
 - unexpected that is, the type of event is not listed in the protocol as an expected occurrence, within 15 days of the CI becoming aware of the event.

Death as a result of disease progression and other events that are primary or secondary outcome measures are not considered to be SAEs and should be reported in the normal way, on the appropriate CRF.

The active monitoring period for (S)AEs will end 13 months after baseline which is after down-titration of study medication. Following the active monitoring period, the CI will report any related or unexpected SAEs that he becomes aware of. Where a participant withdraws consent for further processing of data, this does not preclude the reporting of SAEs. The participant information sheet will include a section explaining this to the participant.

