9.4 Adverse events that do not require reporting

Routine hospitalizations for examinations related to AN standard care will be recorded but do not require reporting.

Additionally, the following known adverse reactions associated with taking olanzapine do not require reporting:

Page 43 of 60

somnolence, weight gain, eosinophilia, elevated prolactin, cholesterol, plasma glucose or HbA1c and triglyceride levels, glucosuria, increased appetite, dizziness, akathisia, parkinsonism, leukopenia, neutropenia, dyskinesia, orthostatic hypotension, anticholinergic effects, transient asymptomatic elevations of hepatic aminotransferases, rash, asthenia, fatigue pyrexia, arthralgia, increased alkaline phosphatase, high gamma glutamyl transferase, high uric acid, high creatine phosphokinase and oedema.

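### Section 9.2 takes unnamed outcome-measure events and disease-progression deaths out of the SAE definition, and 9.4 exempts 28 listed reactions without limiting this to non-serious cases

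*Protocol*

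**What the plan says.** Section 9.1 defines an SAE as "Any adverse event, adverse reaction, or unexpected adverse reaction, respectively, that" results in death, is life-threatening, requires or prolongs hospitalisation, causes persistent or significant disability or incapacity, or is a congenital anomaly. Important medical events are added. No exception is made for cause, or for events that are also study outcomes.

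Section 9.2 requires immediate reporting of all SAEs to the chief investigator and sponsor, "excepting those specified in this protocol as not requiring reporting". It then says that "Death as a result of disease progression and other events that are primary or secondary outcome measures are not considered to be SAEs" and that they "should be reported in the normal way, on the appropriate CRF".

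Section 9.4 adds that "the following known adverse reactions associated with taking olanzapine do not require reporting". The list includes leukopenia, neutropenia, parkinsonism, dyskinesia and orthostatic hypotension.

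For the ethics committee, the 9.2 bullets ask for SAEs that are related and also unexpected. The table of reporting responsibilities in 9.7 asks for SAEs that are related or unexpected, with a copy to the sponsor and the DMEC chair.

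**The concern.** A protocol may route expected events of the disease away from expedited reporting, but it then has to name them. Here the exclusion is defined by reference to the outcome list, and in this study that list is largely a list of safety measurements. An investigator who has to decide whether a suicide attempt, a serious arrhythmia or a severe laboratory abnormality needs an SAE form can find support in the text for either answer. The 9.4 list has a different fault: it exempts reactions by name, whatever their severity.

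The participants are 12 to 24 years old and take olanzapine off-label, in a single-arm study with no comparator. The DMEC is charged with monitoring safety, and examining the quality of adverse-event reporting is itself a secondary objective (3.2). Inconsistent SAE classification between sites would weaken both.

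**Working it through.** No calculation in the protocol bears on this point, so the check sets the sections side by side.

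**1. Does 9.2 contradict 9.1?** A death from disease progression is an untoward medical occurrence in a treated participant and results in death. It is an SAE under 9.1 and is not one under 9.2. That conflict needs no interpretation.

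**2. Which events are outcome measures?** Section 3.5 lists C-SSRS, physical examination, ECG, laboratory parameters and UKU-SERS as secondary measures. Section 10.3.3, under the secondary outcome analysis, lists as safety outcomes the concerning and alerting laboratory and ECG values, other safety parameters, and a summary of AEs and SAEs. Taken literally, 10.3.3 makes SAEs themselves a secondary outcome, so the 9.2 sentence would empty its own category. It cannot be applied consistently without a list of the events meant.

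**3. What does an event lose if it is classed this way?**

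| Route | Section | Depends on SAE status? |
|---|---|---|
| Immediate report to chief investigator and sponsor | 9.2 | Yes: lost |
| Report to ethics committee, copied to DMEC chair | 9.7 table | Yes: lost |
| Olanzapine stopped for a related SAE | 7.10 | Yes: lost |
| Patient-level and trial-level QTc and severe cardiac rules | 7.10 | No: kept |
| Trial stop for "Serious self-harm or suicidal behaviour in more than one patient" | 7.10 | No: kept |
| Entry on the CRF | 9.2 | No: kept |
| Clinician reports and blood results to the chief investigator after each assessment | 10.8 | No: kept |

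The routes that remain follow the assessment schedule: baseline, 8 weeks, 16 weeks, 6 months and 12 months. The longest gap is 12 − 6 = 6 months.

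**4. The 9.4 list.** Counting glucose or HbA1c as one item, and fatigue and pyrexia as two, the list has 28 reactions. One, the aminotransferase elevations, is limited to transient asymptomatic cases. The other 28 − 1 = 27 carry no such limit. Elsewhere the protocol does grade some of these: 6.2 treats a white cell count below 2.0 × 10⁹/L as alerting, and 7.6.2 gives two bands of concern for neutrophils. The 9.2 bracket attaches the exemption to the SAE duty. A participant admitted to hospital with neutropenia or orthostatic hypotension therefore has an SAE under 9.1 that need not be reported under 9.2 and 9.4. Section 9.4 says that routine hospitalisations will be recorded, but gives no such assurance for the listed reactions.

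**5. The ethics-committee criterion.**

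| SAE | 9.2 bullets | 9.7 table |
|---|---|---|
| Related, unexpected | Report | Report |
| Related, expected | No | Report |
| Unrelated, unexpected | No | Report |
| Unrelated, expected | No | No |

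The two rules disagree in two of four cases. The closing paragraph of 9.2, "the CI will report any related or unexpected SAEs", covers the time after active monitoring and names no recipient. The direct conflict is therefore between the bullets and the table.

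**The case against.** The best defence is that an outcome measure is an instrument, not a clinical event. Section 3.5 defines the secondary outcome as completeness and summary statistics of recording these measures. A C-SSRS form is an outcome, and a suicide attempt is not listed as one. On that reading the 9.2 sentence removes little. The reading is open, but 9.2 speaks of events that are outcome measures without saying which, and 10.3.3 calls ECG alerts and SAEs safety outcomes. The ambiguity stands, and so does the conflict over disease-progression deaths.

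A reader might infer that the harms behind the stopping rules would go undetected. The documents do not support this. The trial-stop triggers in 7.10 are written directly on QTc, severe cardiac side effects and self-harm, not on SAE status. ECG and C-SSRS are scheduled at every follow-up visit, and the DMEC reviews accruing data. The 9.4 list contains no QTc, cardiac or self-harm term, so it is a separate defect.

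Nor do the documents say that suicide or sudden cardiac death counts as disease progression. Section 1.1 names them only as the commonest causes of death in anorexia nervosa.

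It would also be too strong to say that the drug's common reactions would vanish from the results. UKU-SERS, ESS, weight and laboratory values are collected on schedule and described under 10.3.3.

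Some safeguards remain. Overdose needs an SAE form (9.5), and SUSARs go to the ethics committee however late they occur (9.7). Section 7.10 lists SARs and SUSARs separately, which may preserve the withdrawal criterion for a related event. Under 9.1 an unusually severe listed reaction may count as unexpected, although 9.2 judges expectedness by type of event. None of these restores prompt reporting of expected serious reactions, or of serious events regarded as outcomes.

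**Conclusion.** The point holds as an internal contradiction in the safety-reporting rules. Following 9.2 and 9.4 as written, an investigator could withhold immediate SAE reporting of a life-threatening event, or one needing hospital admission, that 9.1 defines as serious. For disease-progression deaths and for the 27 listed reactions without a severity limit, this follows from the text. For suicidal, cardiac and laboratory events it rests on one of two open readings of the term outcome measure. The loss is expedited notice, SAE status and the related-SAE withdrawal criterion. Detection at scheduled visits and the trial-stop rules remain. The number of events affected cannot be estimated from the protocol. The matter should be settled because prompt safety oversight of minors on off-label treatment depends on it and the remedy is cheap.

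**What to change.** - **9.2:** delete the sentence on disease-progression deaths and outcome-measure events, or restrict it so that every event meeting a 9.1 seriousness criterion is reported as an SAE, whatever its cause and whether or not it is also an outcome.
- **9.4:** limit the exemption to non-serious occurrences of the listed reactions. State that these are still recorded on the AE form and counted in the 10.3.3 summary.
- **9.2 and the 9.7 table:** use one ethics-committee criterion in both places.
- **7.10:** once 9.2 is settled, check that the withdrawal criteria that refer to SAEs read as the sponsor intends. This review takes no position on the clinical rule.

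The cost is a protocol amendment and a few more AE and SAE forms in 55 patients. No assessment, visit or sample size changes.

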9.3 Premature Termination of the Trial

The trial may be prematurely discontinued by the Sponsor, Chief Investigator on the basis of new safety information or for other reasons given by the Data Monitoring & Ethics Committee / Trial Steering Committee regulatory authority or ethics committee concerned.

If the trial is prematurely discontinued, active participants will be informed and no further participant data will be collected. The Research Ethics Committee will be informed within 15 days of the early termination of the trial.

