9.6 Reporting urgent safety measures

If any urgent safety measures are taken the CI will immediately and, in any event, no later than 3 days from the date the measures are taken, give written notice to the REC of the measures taken and the circumstances giving rise to those measures.

9.7 The type and duration of the follow-up of participants after adverse reactions.

Any SUSAR will be reported to the REC irrespective of how long after administration of Olanzapine the reaction has occurred until resolved.

	Who	When	How	To Whom
SAE (related or	Chief	Within 15 days of CI becoming	SAE Report form for Non-	Main REC with a copy to
unexpected)	Investigator	aware of the event	CTIMPs, available from NRES	the sponsor and DMEC
			website.	Chair
Urgent Safety	Chief	Immediately	By phone	Main REC
Measures	Investigator			
		Within 3 days	Notice in writing setting out	Main REC with a copy sent
			reasons for the urgent safety	to the sponsor. The MREC
			measures and the plan for future	will acknowledge this
			action.	within 30 days of receipt.
Progress Reports	Chief	Annually (starting 12 months	Annual Progress Report Form	Main REC with a copy to
	Investigator	after the date of favourable	(non-CTIMPs) available from the	the sponsor
		opinion)	NRES website	
Declaration of the	Chief	Within 90 days (conclusion)	End of Study Declaration form	Main REC with a copy to
conclusion or early	Investigator	Within 15 days (early	available from the NRES website	the sponsor
termination of the		termination)		
study		The end of study should be		
		defined in the protocol		

Table of reporting responsibilities

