12.11 Post trial care

During this trial, participants will receive olanzapine for 1 year. Following the trial, clinicians will make a shared decision with the patient whether olanzapine will be continued or not. If the clinician and patient decide to end the use of the drug, the dosage will be tapered down gradually for 3-4 weeks before treatment is discontinued completely.

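### Section 9.3 ends all participant data collection on early termination, even for safety, and is not reconciled with the safety follow-up in 9.2, 9.7 and 7.10

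*Protocol*

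**What the plan says.** Section 9.3 lets the sponsor or chief investigator end the trial early "on the basis of new safety information or for other reasons given by the Data Monitoring & Ethics Committee", or at the instance of the steering, regulatory or ethics bodies. On what follows it says: "If the trial is prematurely discontinued, active participants will be informed and no further participant data will be collected". No category of data is exempted.

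Section 7.10 lists events that stop the whole trial. One set is a QTc interval above 500 ms, a rise of more than 60 ms from baseline, or "other severe cardiac side effects in more than one patient". The other is "Serious self-harm or suicidal behaviour in more than one patient".

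Three other provisions bear on follow-up:

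- Section 9.2: "The active monitoring period for (S)AEs will end 13 months after baseline which is after down-titration of study medication". After that, related or unexpected SAEs that come to the chief investigator's notice are still reported. A participant's withdrawal of consent to data processing does not end SAE reporting.
- Section 9.7: "Any SUSAR will be reported to the REC irrespective of how long after administration of Olanzapine the reaction has occurred until resolved".
- Section 7.10, for an individual who stops olanzapine: "every effort should be made to continue to obtain follow up data as long as the participant is willing".

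**The concern.** A stop for safety is the situation in which further adverse event, ECG and suicidality data from exposed participants are most informative. Read literally, 9.3 closes collection at that moment. One participant who stops the drug is followed under 7.10, but if everyone's participation ends because a safety rule was met, 9.3 tells sites to collect nothing more. At stake are the completeness of the safety summary planned in 10.3.3 and a known outcome for the events that caused the stop, both of which would inform a decision about a later RCT.

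**Working it through.** The protocol states no figure on this point, so the check is mainly a comparison of text.

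**1. Is 9.3 limited to non-safety data?** No. It refers to participant data without qualification, in the same section that names safety as a ground for stopping.

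**2. How does the protocol treat stopping the drug elsewhere?**

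| Situation | Section | Data after the drug stops |
|---|---|---|
| Individual stops olanzapine | 7.10 | Follow-up continues if the participant is willing |
| Pregnancy | 9.1 | Followed to 12 months after baseline |
| Overdose | 9.5 | May remain in the study to 12 months |
| Consent to data processing withdrawn | 9.2 | SAE reporting continues |
| Whole trial stopped | 9.3 | None |

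Section 7.13.2 does withdraw a participant in case of pregnancy, so that row has its own inconsistency. Even so, 9.3 is the only one of these provisions that ends collection outright.

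**3. Which data have a route if 9.3 is applied literally?**

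- SUSARs: 9.7 keeps reporting to the REC open until resolution.
- Other SAEs: 9.2 can be read as keeping reporting alive, but 9.3 points the other way.
- Non-serious AEs: 9.2 covers them up to 13 months if it prevails. If 9.3 prevails, they have no route.
- Trigger events that are not SUSARs: these are exposed. A QTc rise without symptoms may meet none of the listed seriousness criteria in 9.1, although the important-medical-event clause there might apply. Section 9.2 also says that events which are primary or secondary outcome measures are not treated as SAEs and go on the CRF. Section 3.5 lists ECG and C-SSRS among the secondary measures. On that reading, QTc and suicidality findings are recorded on the CRF, which is what 9.3 closes.

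**4. Which rule prevails?** No section says. Section 7.12 ties database lock to the 12-month assessment of the 55th patient and does not cover an early stop.

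**5. How likely is a stop?** The threshold is two patients, and 2/55 = 3.6%. That is the size of the trigger, not its probability. The protocol gives no event rate. If q is an assumed per-patient risk of meeting one criterion, with all 55 enrolled and fully followed,

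P(at least 2 of 55) = 1 − (1 − q)^55 − 55·q·(1 − q)^54.

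| Assumed q | P(at least 2 of 55) |
|---|---|
| 1% | 10.5% |
| 2% | 30.1% |
| 3% | 49.4% |
| 5% | 76.8% |
| 10% | 97.8% |

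For q = 1%: 1 − 0.575 − 0.320 = 0.105. The spread shows that the answer depends almost wholly on q, so the table illustrates and does not estimate.

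**The case against.** The best defence is that 9.3 sits in the pharmacovigilance chapter between 9.2 and 9.7, neither of which lapses by its terms when the trial ends. It can then be read as ending research assessments while safety reporting duties continue. Participants also stay under their specialist team (7.13.2), so recording is at risk and not care. Section 2.4 says the study is not meant to establish safety or efficacy, and the sentence operates only after an early stop.

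Much of this stands, and it rules out three stronger readings that a reader might infer:

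- *That harms after a stop would never be captured.* Sections 9.2 and 9.7 can be read as keeping SAE and SUSAR reporting alive.
- *That a whole taper would go unobserved in all 55 participants.* The sentence "the dosage will be tapered down gradually for 3-4 weeks before treatment is discontinued completely" (12.11) concerns the period after the one-year trial, if clinician and patient decide to end the drug. Section 8.7 likewise ties down-titration to month 12. No taper is described for an early whole-trial stop, and 55 is only a ceiling, since a stop could come before full enrolment or after some participants have finished.
- *That a threshold of 3.6% shows a stop to be likely.* It does not. The exclusions for QTc, suicidality and serious self-harm in 6.2 should lower the risk.

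The defence does not remove the conflict. It has to supply a limit that 9.3 does not contain. Section 9.7 covers only SUSARs, and once the active period ends 9.2 relies on what the chief investigator happens to learn.

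**Conclusion.** The point holds as an internal contradiction. Section 9.3 conflicts with 9.2 and 9.7, and with the approach 7.10 takes to individuals, and the protocol gives no order of precedence. After a safety stop, collection of non-serious AEs and of the course of trigger events that are not SUSARs is not secured. The 10.3.3 safety summary could end at the stop date with open events lacking an outcome, and 10.7 plans no imputation or other handling of missing data.

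At most 55 participants are affected, and only if the trial stops early. No probability of that can be taken from the protocol. The conclusion assumes that sites would follow 9.3 as written. It does not depend on the cardiac rule alone, which 3.3.7 words differently by placing the stop after the feasibility phase: 9.3 applies to any safety stop, and 7.10 also has the self-harm rule. The primary feasibility analysis plan is unaffected. This should be corrected, but it does not undermine the study.

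**What to change.** Reconcile 9.3 with 9.2 and 9.7:

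- Limit the 9.3 sentence to recruitment and non-safety research assessments.
- State that AE and SAE collection for exposed participants continues for the monitoring period set in 9.2, which is a fixed point 13 months after baseline, and that SUSAR reporting continues under 9.7.
- Add that 7.10 trigger events and other SAEs open at termination are followed to outcome. This would be new text, because 9.7 covers SUSARs only.
- Hold database lock for these data.

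The amendment should also say who records follow-up of a self-harm trigger. The schedule in 3.7 assigns C-SSRS to the researcher alone, whereas ECG is shared with the clinical team, so routine care may yield few C-SSRS data once research visits end.

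The cost is a short amendment, a line in the information sheet and, only if the trial stops early, limited adverse event collection and a later lock. How treatment is ended after an early stop is a clinical matter and is not addressed here.
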